### **Scientific Rationale/ Background**

Inhaled medications are the cornerstone of therapy for respiratory airways diseases such as asthma and COPD, delivering medication directly to the organ of concern and allowing for reduced systemic exposures and side effects of needed drugs. Since medication delivery to the lungs is essential for this form of therapy, the delivery device chosen plays a critical role in the effectiveness of these medications.

Multiple factors can lead to ineffective handheld inhaler drug delivery, including components unique to how the drug is compounded, unique characteristics of each delivery device and various individual patient limitations (e.g cognitive impairment, mechanical usage difficulties in patients with arthritis and neuromuscular diseases, and respiratory muscle dysfunction).

Dry powder inhalers (DPIs) are one of the most common handheld delivery systems used by respiratory patients and present with many unique features. Importantly, they are breath actuated, which helps many patients with timing and ease of device use. However, DPIs require a certain level of inspiratory effort to create an inspiratory flow sufficient to inhale the medication from the inhaler and disaggregate the medication from its excipient carrier creating respirable medication particles needed for effective drug delivery.

Failure of effective drug delivery will lead to failure of whatever clinical outcome for which an inhaled device is being used. It has recently been suggested that a low peak inspiratory flow (PIF) during DPI usage can contribute to inpatient and outpatient treatment failures in patients with COPD. Indeed, a subset of patients with low PIF in an observational hospital study were noted to have higher readmission rates when treated with a DPI compared to those treated with nebulizers. However, other investigators have observed that a low PIF is a minor clinical problem in outpatients and inpatients with COPD. Overall, specific information about how PIF measurements are made and how they relate to therapeutic and clinical responses in the use of DPIS for COPD patients is lacking.

### **Peak Inspiratory Flow (PIF)**

Ohm's law defines the relationship between inspiratory pressures, inspiratory airflows and resistances. For any given resistance, the level of airflow generated is directly dependent on the pressure gradient across the resistance. In the case of DPIs, each device has a defined fixed resistance. Thus, the inspiratory flow generated is directly related to the inspiratory pressure applied to the device. The inspiratory pressure generated, in turn, depends on the degree of effort applied by the patient, the manner in which the effort is performed and any medical conditions that might reduce or limit a patient's capabilities to generate an inspiratory muscle force (even with a maximal effort).

Identifying the level of effort required to properly use a DPI is further challenged by the multiple different DPIs that are commercially available, each having different resistances and varying instructions for how to inhale when using the device. Clinical patient data is limited related to the degree of effort and flow needed by a patient for effective drug delivery for any given DPI, with even less known about the clinical consequences of inadequate DPI usage.

Various patient characteristics have been suggested that might predict patients with risk for poor inspiratory flow capabilities leading to impaired DPI medication delivery, including female gender, short stature, severe airflow limitation and lung hyperinflation. However, none of these are sensitive and specific enough to prospectively identify patients in a clinical situation who may not be able to effectively use a DPI.

Inspiratory flow rates are often measured as a part of spirometry and these measurements might be useful to identify patients who are unable to generate inspiratory airflows sufficient to effectively use a DPI. However, airflows measured during spirometry are obtained using a large bore mouthpiece with virtually no resistance and peak inspiratory flows measured during spirometry maneuvers have been suggested to not correlate well with inspiratory airflows achieved when inspiring through a resistance typically found in a DPI.

### **InCheck Dial Device**

Recently, it has been suggested that the InCheck Dial, a device originally designed to train and coach patients on how to use their inhalers correctly, might be used to determine whether a patient's peak inspiratory flow (PIF) is sufficient for effective DPI drug delivery, by maximally inspiring through a resistance appropriate to the DPI being used by the patient. It has also been suggested that there may be a suboptimal PIF below which effective medication delivery from a DPI begins to drop, leading to a risk of a lower clinical effectiveness. A minimal or critical PIF has also been suggested, below which no medication is effectively delivered. Since DPI devices have varying resistances, measured PIF will vary based on the resistance against which it was measured, with implications for suboptimal and minimal PIF changing accordingly.

Nevertheless, the concept of suboptimal PIF as a tool to help identify patients who might not be able to effectively use a DPI and that an alternative delivery system should be considered for their respiratory medications is reasonable.

### **PIF Measurement Technique**

Before any diagnostic tool can be used in clinical practice, it must meet criteria showing the robustness of the test and defining any limitations that the test may have. Ideally, test sensitivity, specificity, positive and negative predictive values and receiver operator characteristics (ROC) should be determined. In the case of PIF, none of these qualities have been determined to date. In spite of this and based on modest data from drug impactors and limited observational studies, it has been suggested that a PIF of <60 l/min is suboptimal and a PIF <30 l/min is minimal for DPI usage. Recommendations about the use of PIF to dictate device selection has also been made based on these results.

Critical questions remain for PIF, including at what resistance it should be measured and exactly how the PIF effort should be performed. To be most meaningful, the effort should mimic the effort used when the patient inhales with their DPI, which should match the effort recommended by the DPI device maker, and the outcome measured should relate to the expected clinical response desired for the medication being used.

Common variables that change with patient inspiratory effort include the intensity, speed, depth and duration of the inspiratory effort. Each can change the pressure applied to the DPI and alter the inspiratory flow. By definition, one might assume that PIF would best be measured as a maximal effort, since it is “peak”. However, to achieve such a “peak” measurement, one needs to inhale with a very sharp, rapid, intense effort starting from residual volume (RV). Although breathing down to RV provides maximal stretch of the respiratory muscles and offers their greatest force generation, breathing down to RV can be difficult. Lesser degrees of forced exhalation prior to a PIFR effort would then be expected to provide a lower “PIF” measurement, even when otherwise performing a sharp, maximal efforts. On the other hand, a sharp, maximal effort may give a “peak” inspiratory flow, but might not be able to effectively performed during routine DPI usage and may go against device maker recommendations for their DPI usage. An intense “peak” effort could also lead to increased oropharyngeal drug impaction, reducing the amount of medication delivered to the lower airways.

What level of reproducible effort is needed to provide a reliable PIF measurement is also uncertain. Three efforts has been suggested, but the variability allowed between efforts and whether the best or average PIFR should be used is also unclear. These decisions become critically important when performing “effort-dependent” testing, since variable submaximal efforts will give inadequate results and could inappropriately define a patient with a “suboptimal” PIF when, in fact, they are fully capable of inhaling sufficiently to use a DPI.

### **Study Purpose**

The purpose of this research is to determine whether PIF is clinically important when using the Ellipta DPI device. In addition, the study will validate the best/most clinically appropriate way to perform a PIF maneuver, to determine the testing capabilities of the preferred PIF maneuver and to relate this PIF measurement to meaningful clinical outcomes in COPD patients.

### **Hypothesis**

A standardized method for determining PIFR can be developed

- to determine if low PIF is a meaningful clinical problem in patients with COPD using the Ellipta DPI
- to identify what clinical features predict a risk of inadequate response to an inhaled medication delivered by the Ellipta DPI
- to detect the presence, prevalence and risk of low PIF in patients with COPD
- to identify what clinical features in COPD patients may predict a lower PIF

## **Objectives/Questions**

### **Primary**

- Determine if an inhaled short acting bronchodilator delivered by a non-DPI delivery device (Ventolin pMDI with a spacer) produces added clinical bronchodilation added to Trelegy has been delivered by the Ellipta DPI if a suboptimal or minimal PIF is present in COPD patients.

### **Secondary**

- Determine if a suboptimal or a minimal PIF in COPD patients predicts clinical response to medication delivered using the Ellipta DPI device.
- Determine the best way to measure PIF for the Ellipta device and are there suboptimal or minimal PIF thresholds that can be identified to predict response to a DPI?
  - What inspiratory effort should a patient exert when measuring PIF?
  - What lung volume should a patient start from when measuring PIF?
  - What reproducibility criteria should be used when measuring PIF?
- Determine if best PIF correlates with FEV1, FVC, IC or peak inspiratory flow measured during spirometry.

### **Study Population**

- outpatients of either sex
- age  $\geq 40$  years with a clinical diagnosis of COPD
- smoking history  $>10$  pack years
- post-bronchodilator FEV1  $<50\%$  predicted
- post-bronchodilator FEV1/FVC  $<70\%$
- female participants are eligible to participate if they are not pregnant, not breastfeeding, and at least one of the following conditions applies:
  - not a woman of childbearing potential OR
  - agree to follow the contraceptive guidance during the treatment period and until the safety follow-up contact after the last dose of study treatment
- stratification requiring at least 1/3 of patients having a PIF of  $< 60$ L/min (AM pre-dose based on using the level 2 InCheck Dial resistance setting with a sharp maximal effort starting after exhaling fully)

### **Exclusion Criteria**

- any subject with unstable disease, including
  - COPD exacerbation in the last 6 weeks
  - upper respiratory tract in in the last 4 weeks
  - COPD or upper respiratory tract infection during run-in  
(subjects may be re-screened x 1 when stable after an acute event)
  - pulmonary disease other than COPD
  - any lung resection
  - unstable cardiac conditions  
(at the discretion of the investigator)
  - other unstable medical conditions  
(at the discretion of the investigator)

- participants who are medically unable to withhold their albuterol/salbutamol for the 4-hour period required prior to spirometry testing at each study visit
- participants who are unable to perform acceptable study test maneuvers
- women who are pregnant or lactating or are planning on becoming pregnant during the study
- a history of allergy or hypersensitivity to any corticosteroid, anticholinergic/muscarinic receptor antagonist,  $\beta_2$ -agonist, lactose/milk protein or magnesium stearate or a medical condition such as narrow-angle glaucoma, prostatic hypertrophy or bladder neck obstruction that, in the opinion of the Investigator, contraindicates study participation
- risk factors for pneumonia: immune suppression (e.g. advanced human immunodeficiency virus [HIV] with high viral load and low CD4 count, collagen vascular diseases on immunosuppressants) or other risk factors for pneumonia (e.g. neurological disorders affecting control of the upper airway, such as Parkinson's Disease, Myasthenia Gravis) that in the opinion of the investigator would increase risk of pneumonia
- participants at risk of non-compliance, unable to comply with the study procedures and the proposed treatment regimen, or have any infirmity, disability, or geographic location that would limit compliance for scheduled visits

#### **Study Design and Methods Rationale**

- The expected FEV1 response to a bronchodilator is uncertain as multiple factors influence this measure, including severity of disease, day to day variability, varying reversibility in COPD patients, the delivery of the drug to a patient and the effectiveness of the medication delivered. Thus, the measurement of an acute bronchodilator response after delivering a long acting bronchodilator may not identify whether a medication has been effectively delivered to a patient.
- However, if a long acting bronchodilator has not been effectively delivered to the lung, then subsequent delivery of a short acting bronchodilator should produce a significant additional bronchodilator response. On the other hand, if a long acting bronchodilator has been effectively delivered to the lung, then subsequent delivery of a short acting bronchodilator should not produce any further significant bronchodilation.
- Based on this rationale, comparison of the acute bronchodilator response to a short acting bronchodilator after receiving a long acting should identify whether drug delivery is ineffective in a selected patient population, irrespective of baseline FEV1 and of any partial response to the long acting bronchodilator. Comparison of the short acting bronchodilator measurement between patient groups with differing PIF thresholds should identify whether PIF has an impact of drug delivery of a long acting bronchodilator via a DPI.
- **Open label design comparing the acute bronchodilator response after delivery of a long acting bronchodilator via Ellipta DPI in patients with normal, suboptimal and minimal PIF.**

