### **Visit 1**

#### **Consent**

#### **Baseline Measurements**

- Demographics
- History and Physical
- CAT
- Exacerbation history in the last year (# moderate and # severe)
- Pre Ventolin PIF measured with the Incheck Valve set to a low/mid level 2 resistance and measured after instructions to exhale fully followed by a sharp maximal inhalation (minimum of 3 efforts)
- Pre and 15-30 minutes Post Ventolin spirometry

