#### **Study Endpoints**

##### **Primary**

- Post BD response to Trelegy Ellipta at Visits 2 and 3 by PIF (normal, suboptimal, minimal)
- Post BD added response to Albuterol after Trelegy Ellipta at Visits 2 and 3 by PIF (normal, suboptimal, minimal)

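### A small added Ventolin response is read as evidence that Trelegy was delivered, but patients with little albuterol reversibility show one even when delivery fails, and the Visit 1 Ventolin change is not used in any analysis

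*Combined protocol and SAP*

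**What the plan says.** Study Design and Methods Rationale sets out two rules. If the long-acting drug did not reach the lung, "subsequent delivery of a short acting bronchodilator should produce a significant additional bronchodilator response". If it did, "subsequent delivery of a short acting bronchodilator should not produce any further significant bronchodilation". The section concludes that the response to the short-acting drug should identify ineffective delivery in a patient population, "irrespective of baseline FEV1 and of any partial response to the long acting bronchodilator", and that comparing PIF groups on it should show whether PIF matters.

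The first bullet of the same section explains why the response to the long-acting drug is hard to interpret. The reasons include "varying reversibility in COPD patients, the delivery of the drug to a patient and the effectiveness of the medication delivered".

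Other relevant text:

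- **Study Population** sets upper limits on post-bronchodilator FEV1 and FEV1/FVC, with no minimum reversibility.
- **Visit 1, Baseline Measurements** collects "Pre and 15-30 minutes Post Ventolin spirometry". The post-Ventolin value serves the entry limits; no use is given for the change.
- **Study Endpoints, Primary** lists the response to Trelegy and then "Post BD added response to Albuterol after Trelegy Ellipta at Visits 2 and 3 by PIF (normal, suboptimal, minimal"). Both are split by PIF group only.
- **Study Endpoints, Secondary** includes predictors of the Trelegy response, but names no candidates and does not extend to the added Ventolin response.
- **Statistical Plan of Analysis** names no covariate, interaction or subgroup.

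**The concern.** Reading a small added response as delivery is the contrapositive of the first rule, and it is valid only if the patients could respond to albuterol. The rationale names "varying reversibility in COPD patients" as a reason to distrust the Trelegy response, then does not apply it to the Ventolin response. The scope claimed for the rule covers baseline FEV1 and partial Trelegy response but says nothing of reversibility.

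This is a problem of assay sensitivity. Low reversibility pulls the PIF contrast toward zero, which is the direction that supports a conclusion that low PIF does not impair Ellipta delivery. The Statistical Plan of Analysis intends to assess non-inferiority and to supply estimates for future studies, so a diluted contrast could be carried forward as an estimate of the effect on delivery.

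**Working it through.** **Inputs.** From the protocol: 30 patients, 10 to 15 of them with PIF below 60 L/min (Number of subjects); 50 ml as a non-inferiority level and 140 ml as the within-subject SD of a cited comparative study (Statistical Plan of Analysis). Assumed, because the documents give no figure: the fraction f unable to respond to albuterol, 30% to 60%, and the response R of those who can. The plan has no figure of its own on this point to reproduce.

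**Step 1: logic.** Cross delivery with reversibility:

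| | Can respond to albuterol | Cannot respond |
|---|---|---|
| Trelegy delivered | no added response | no added response |
| Delivery failed | added response | no added response |

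Three of the four cells show no added response, and one of them is complete delivery failure.

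**Step 2: dilution with f equal across groups.** Let F be the share of a PIF group in whom delivery fails. The group mean added response is R × (1−f) × F. If everyone could respond, the difference between groups would be D = R × (F_low − F_normal). With fraction f unable to respond it is (1−f) × D.

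- f = 0.30: 0.70 × 100 ml = 70 ml
- f = 0.60: 0.40 × 100 ml = 40 ml

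Above f = 50%, a true 100 ml difference falls below 50 ml. Of 10 low-PIF patients, 10 × (1−f) = 7 to 4 could reveal a failure.

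**Step 3: bias with f unequal.** Take R = 150 ml (illustrative).

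- Low PIF, F = 100%, f = 75%: 150 × 0.25 × 1 = 37.5 ml
- Normal PIF, F = one third, f = 25%: 150 × 0.75 × 1/3 = 37.5 ml

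The contrast is zero although failure is three times as frequent in the low-PIF group.

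**Step 4: why a main-effect covariate is not enough.** Let R_i be patient i's capacity to respond. The expected added response is F × R_i, so the difference between PIF groups at capacity R_i is (F_low − F_normal) × R_i. It grows with capacity. An additive term removes imbalance in R_i but still estimates one average difference, which remains diluted. The interaction of PIF group with R_i carries the information on delivery.

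**Step 5: why not select on the Visit 2 pre-dose to post-Ventolin gain.** That gain and the added response share the post-Ventolin FEV1. Suppose a patient responds to neither drug, measurement errors are equal and independent, and a change has SD 140 ml (assumed).

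- Chance of passing a 50 ml cut: P(Z > 50/140) = P(Z > 0.357) = 36%.
- Mean gain among those who pass: 140 × φ(0.357)/0.36, about 145 ml.
- The added response has covariance with the gain equal to half the gain's variance, so its mean among those who pass is about 145/2 = 73 ml.

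The cut would create an apparent added response in patients who have none.

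**The case against.** The strongest case on the other side has five parts.

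1. **The plan scores no individual.** A reader might infer that each non-reversible patient is counted as a delivery success, or that the plan claims proof of delivery. The text supports neither: it compares groups and says the comparison should identify ineffective delivery. This stands, and the point is confined to the group contrast.

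2. **Dilution is partly the true answer.** The primary objective asks whether Ventolin adds clinical bronchodilation after Trelegy. Patients who cannot dilate gain nothing, so (1−f)D is the correct average for that question. This stands; only the delivery interpretation is affected.

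3. **The other primary endpoint helps.** A patient flat to both drugs can be told apart from one who responds to Trelegy and then gains nothing from Ventolin. True, but in the flat patient neither endpoint shows whether the drug arrived.

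4. **Visit 1 is not a clean measure of reversibility.** Maintenance washout is listed at Visit 2 and not at Visit 1. A small Visit 1 change may reflect residual maintenance drug. A larger change in low-PIF patients may itself reflect failed delivery from a maintenance DPI. It is therefore tempting, but unsupported, to treat the Visit 1 change as an own-control test showing that PIF marks reversibility rather than delivery. This stands and shapes the fix.

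5. **The study is declared exploratory and probably underpowered.** That concedes imprecision. It does not repair the inference, since more patients would only narrow the interval around a diluted value.

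**Conclusion.** The concern holds for the inference about delivery. As written, the rationale would let a null PIF contrast be read as equal delivery without regard to whether the patients could respond to albuterol, and nothing elsewhere in the protocol supplies that qualification.

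The size depends on f, which is an assumption. At 30% to 60%, equal across PIF groups, a 100 ml difference would appear as 70 to 40 ml. If f differs by PIF group, the bias can hide a real difference. The calculation treats capacity as all or nothing with a common R; graded capacity gives the same kind of dilution.

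A reader might go further and conclude that the primary contrast is invalid. The documents do not support that, because the average added response in all 30 patients remains the right quantity for the stated primary objective.

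**What to change.** 1. **Amend Study Design and Methods Rationale.** State that the absence of a difference in added response between PIF groups is evidence of equal delivery only to the extent that the patients showed capacity to respond to albuterol. Remove the implication that the rule holds regardless of reversibility.

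2. **Keep the primary contrast in all 30 patients and add one prespecified exploratory analysis.** Model the added response with the Visit 1 Ventolin FEV1 change as a continuous variable, PIF group, and their interaction.

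3. **Tabulate the Visit 1 Ventolin change by PIF group**, beside maintenance drug, device and time since last dose. Label the table descriptive, for the reasons given on Visit 1 above.

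Do not define responders by a 50 ml cut: the protocol cites 50 ml as a non-inferiority level between bronchodilators, not as a threshold for reversibility. Do not select patients on the Visit 2 pre-dose to post-Ventolin gain.

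The cost is a change of wording, one model and one table. Time since last maintenance dose must be noted at Visit 1 if the history does not already capture it. The interaction estimate will be imprecise at n = 30 and should be reported with its interval and no claim of confirmation.
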